4.2.4.3 Day 15 (± 1), All Cycles (Cohort 11)

On Day 15, the procedures listed below will be performed:

- Vital signs: temperature, weight, blood pressure, heart rate and respiratory rate;
- Symptom-driven physical examination
- Clinical laboratory tests (hematology, clinical chemistries)
- **Cycles 1 and 2:** Collect PD specimens (biomarker & PBMC) at Day 15 bag change.
- **Cycle 1 only:** Collect a single PK at the Day 15 bag change.
- Adverse Event and concomitant medication assessment

4.2.4.4 Day 21 (± 1) (Cohort 11)

The procedures listed below will be performed:

- Bag change for TK216
- Vital signs
- Symptom-driven physical examination
- Clinical laboratory tests (hematology, clinical chemistries)
- **Cycles 1 and 2:** Collect single PK only
- Adverse events and concomitant medication assessment

4.2.4.5 Day 28 (± 1), All Cycles (End of Infusion) (Cohort 11)

On Day 28, the procedures listed below will be performed:

- Vital signs: temperature, weight, blood pressure, heart rate and respiratory rate;
- Symptom-driven physical examination
- Clinical laboratory tests (hematology, clinical chemistries)
- **Cycles 1 and 2:** Collect PD specimens (biomarker & PBMC) at the end of infusion.
- **Cycle 1 and 2:** Collect a single PK at the end of infusion.
- Adverse Event and concomitant medication assessment

If Day 28 and Day 1 of the next cycle occur on the same day, please add the assessments below:

- TK216 infusion via a central venous catheter will be initiated (preferred). TK216 infusion via a peripheral line is allowed; infusion will continue for 28 days
- ECOG or Karnofsky/Lansky performance status**;
- Additional clinical laboratory tests (coagulation, urinalysis)**;
- For woman of childbearing potential, a urine pregnancy test

4.2.4.6 Rest Period, All Cycles, if needed (Cohort 11)

There is no mandatory or pre-specified rest period. If TK216 administration is paused, every seven days (± 1 day) after the TK216 infusion is stopped, the procedures listed below should be performed.

- Clinical laboratory tests (hematology);
- AE and concomitant medication assessment;
- The clinical laboratory testing may be done at a local laboratory, and the interview may be conducted by telephone.
- If the rest period is greater than 7 days ($+1$); an optional pre-dose PK sample may be requested.

When the patient re-starts, Day 1 assessments should be completed and continued eligibility should be assessed.

4.2.5 Early Termination/End of Treatment Visit, Cohort 11

For all patients in Cohort 11, an End of Treatment Visit will be conducted within 7 days after treatment discontinuation, and a Safety Follow-Up visit will be conducted approximately 28 days following the last day of TK216 infusion. The following procedures will be performed at the End of Treatment Visit:

- ECOG performance status
- Vital signs;
- Weight;
- For pediatric patients, height
- Complete physical examination;
- 12-lead ECG;
- Clinical laboratory tests (hematology, clinical chemistries, coagulation, urinalysis);
- Collect PD specimens (biomarker & PBMC);
- Urine pregnancy test: women of child-bearing potential only;
- If a CT scan or MRI has not been completed within 6 weeks, it should be done at this visit. The same method of assessing disease must be used throughout the study;
- Concomitant medication check;
- Adverse event assessment.

4.2.6 **TK216 Therapy Following Disease Progression (Part 4)**

Patients may rapidly develop tumor-related symptoms even in the face of stable or minimally progressive disease. Therefore, as of Protocol version 7.0, palliative local radiation therapy may be allowed if the following criteria are met:

1. Treatment is required for a symptomatic, non-target lesion(s) (example: pain due to compression of nerve in a closed space).
2. Planned radiation therapy is focal and the field does not involve the treatment of target lesion(s) directly or indirectly by an inability to fully shield adjacent target lesions from any radiation effect.
3. There is a reasonable possibility that the patient will benefit from additional systemic therapy with TK216.
4. Approval for this treatment has been granted by Oncternal.

4.2.7 **Post-treatment follow-up**

A Safety Follow-Up telephone call will be conducted approximately 28 days following the last day of TK216 infusion, if the infusion is terminated early; or approximately 28 days after the completion of the last cycle which the patient completes. Additionally, each patient will be contacted by telephone or email approximately every 3 months following study discontinuation until death, loss to follow-up, or withdrawal of consent in order to assess disease progression and survival status. A review of the medical record may also be performed if applicable to assess disease progression and survival status.

4.2.8 **Patient withdrawal criteria and procedures**

A patient will be permanently discontinued from study treatment if the patient develops a toxicity or concurrent illness that, in the investigator's judgment, precludes further treatment with the study drug.

A patient may be permanently discontinued from the study for any of the following reasons:

- Intolerable adverse event that does not improve with dose adjustments

- significant abnormal clinical laboratory values that are possibly, probably or certainly attributed to study drug. This includes Grade 3 or greater laboratory abnormalities that do not improve to \leq Grade 1 or baseline severity within 4 weeks of the last dose received.
- pregnancy
- non-compliance (not completing all required assessments at required times, missing scheduled visits, high frequency of missed doses, refusing to complete duration of dosing) or protocol violation
- patient withdraws consent and refuses to participate in the study
- investigator's or sponsor's decision that withdrawal is in the patient's best interest
- termination of the study by the sponsor (see Section 10.7)
- RECIST, version 1.1-defined disease progression is observed

If for any reason, a patient is discontinued from study before the patient completes 1 cycle of treatment; all assessments outlined in the Flow Chart of Study Assessments in the Study Synopsis and listed in Section 6.3.10 are to be completed. The reason(s) for a patient's discontinuation of treatment or withdrawal from the study will be clearly documented in the source documents and on the CRF. Any patient who completes Cycle 1 will be considered to have completed the study.

7 Study Drugs

7.3 Pharmaceutical information

7.3.4 TK216

7.3.4.1 Description

TK216 is a small molecule inhibitor of the EWS-FLI1 fusion protein, and other related *ets*-family member proteins that are implicated in the pathogenesis of Ewing sarcoma.

7.3.5 Vincristine

7.3.5.1 Description

Vincristine is an alkaloid isolated from *Vinca rosea* Linn (periwinkle). It binds to tubulin, disrupting microtubules and inducing metaphase arrest. Its serum decay pattern is triphasic. The initial, middle, and terminal half-lives are 5 minutes, 2.3 hours, and 85 hours respectively; however, the range of the terminal half-life in humans is from 19 to 155 hours. The liver is the major excretory organ in humans and animals; about 80% of an injected dose of vincristine sulfate appears in the feces and 10% to 20% can be found in the urine. The p450 cytochrome involved with vincristine metabolism is CYP3A4. There is poor CSF penetration.

Common toxicities include alopecia, constipation and loss of deep tendon reflexes. Occasional toxicities include jaw pain, headache, weakness, abdominal pain, mild myelosuppression, peripheral paresthesias, wrist drop, foot drop and abnormal gait.

Fetal toxicities and teratogenic effects of vincristine (either alone or in combination with other antineoplastic agents) have been noted in humans. The toxicities include: chromosome abnormalities, malformation, pancytopenia, and low birth weight. It is unknown whether the drug is excreted in breast milk.

A complete description is found in the prescribing information (Pfizer, 2013)

7.3.5.2 Dosage form, strength and route of administration

Vincristine Sulfate Injection, USP is a sterile, preservative-free, single use only solution available for intravenous use in 2 mL (1 mg and 2 mg) vials. Each mL contains 1 mg Vincristine Sulfate, USP, 100 mg mannitol and Water for Injection, USP. Q.S. Sulfuric acid or sodium hydroxide have been added for pH control. The pH of Vincristine Sulfate Injection, USP ranges from 4.0 to 5.0. At the time of manufacture, the air in the containers is replaced by nitrogen (Pfizer, 2013).

7.3.5.3 Supply and stability information

Vincristine will be obtained from the site pharmacy.

7.3.5.4 Administration guidelines

The intrathecal administration of vincristine sulfate injection usually results in death. To reduce the potential for fatal medication errors due to incorrect route of administration, Vincristine sulphate injection should be diluted in a flexible plastic container and prominently labeled as indicated for intravenous use only. Syringes containing this product must be labelled, using the auxiliary sticker provided, to state “FOR INTRAVENOUS USE ONLY – FATAL IF GIVEN BY OTHER ROUTES.”

Vincristine Sulfate Injection, USP when diluted with 0.9% Sodium Chloride Injection in concentrations from 0.0015 mg/mL to 0.08 mg/mL is stable for up to 24 hours when protected from light or 8 hours under normal light at 25°C (Pfizer, 2013).

Injection of vincristine sulfate should be accomplished as per institutional policy. Vincristine sulfate must be administered via an intact, free-flowing intravenous needle or catheter. Care should be taken to ensure that the needle or catheter is securely within the vein to avoid extravasation during administration.

7.4 Procedures for monitoring patient compliance

Calculations of the dose administered will be documented in the source documents at the site and confirmed during monitoring visits by the clinical monitor. In addition, the dose administered will be documented in the electronic CRFs. Any interruptions or discontinuations of the infusion will be documented in both the source documents and the electronic CRFs.

7.5 Accountability

Master drug accountability forms will be used to maintain accurate records of receipt, distribution, and return of all drug supplies shipped to the site from the sponsor’s representative. A drug accountability form will be maintained at each location where drug is stored for patient administration, i.e., main pharmacy, satellite pharmacy, physician’s office or other dispensing areas. Individual patient drug accountability forms will be used to maintain accurate records of drug dispensed, returned and consumed by each patient.

When the clinical site receives supplies of TK216 and the custom diluent from the sponsor, or its representative, a visual inspection of the drug will be conducted and the condition of supplies will be recorded. Any damaged or missing supplies are to be reported on the accountability forms. The date, investigational drug lot numbers and/or vial numbers, and the amount of drug received will be documented on a master drug accountability form. During the course of the study, the initials and number of each patient to whom drug is dispensed, the date, quantity of drug dispensed, all transfers, returns, and disposal/destruction of drug are to be documented on the accountability forms.

Drug supplies will be stored in a secure, limited-access storage area under the recommended storage conditions. Regular periodic inventory of the investigational drug supply will be performed.

8 Ethical Considerations

8.3 Institutional Review Board (IRB)/Independent Ethics Committee (IEC)

The IRB/IEC is responsible for the review and approval of relevant study documentation to assure the protection of the rights and welfare of human patients. Relevant documents requiring review and approval by an IRB/IEC include but are not limited to; the study protocol and amendments, the patient written informed consent form and consent form updates, patient recruitment documentation (e.g., advertisements), written information provided to patients, Investigator's Brochure (IB) and any revisions or Addenda, available safety information, patient payment/compensation, investigator's current curriculum vitae (or other qualification documentation), and any other documents that the IRB/IEC may need to fulfill its responsibilities. The IRB/IEC is required to operate in compliance with current regulations of the local regulatory authorities, the International Conference on Harmonisation (ICH) guidelines and current Good Clinical Practice (cGCP) guidelines. Written approval from the IEC must be obtained before the study can be started (consent of the first patient) or before the investigational study drug is administered to a patient.

Changes to the study requiring an amendment to the protocol or changes to the informed consent form; must be approved in writing by the IRB/IEC. IRB/IEC approval must be obtained prior to the implementation of such changes.

The sponsor or representative will report promptly to the investigator any new information that may indicate an adverse effect on the safety of the patients or the conduct of the study. The investigator is responsible for informing the IRB/IEC of any new safety information (e.g., safety report presented as an IB Addendum), and for reporting the progress of the study. At the end of the study, defined as the last visit of the last patient, the investigator will provide a final report to the IRB/IEC (if required).

8.4 Ethical Conduct of the Study

The clinical study will be conducted in accordance with the ethical principles that have their origin in the Declaration of Helsinki (in its revised edition, Tokyo 2004), and that are consistent with the guidelines for current Good Clinical Practice (cGCP) and applicable regulatory requirements.

8.5 Informed Consent

The principal investigator is responsible for ensuring that no patient undergoes any study-related examination or activity before that patient has given written informed consent to participate in the study. The patient must give the written consent only after detailed information about the study has been provided. The verbal explanation will cover all the elements specified in the written information provided to the patient.

An investigator or representative will inform the patient of the aims, methods and potential hazards of the study. The patient must be given every opportunity to clarify any points he/she does not understand and, if necessary, ask for more information. At the end of the informed consent discussion, the patient will be given time to consider the study information and to freely decide his/her participation. If the patient agrees to participate in the study, the informed consent document must be

signed by both the patient and by the person who conducted the informed consent discussion. A copy of the signed consent will be given to the patient and the original will be archived in the investigator site file.

It should be emphasized to the patient that he/she is free to withdraw from the study at any time. Patients who refuse to give or who withdraw written informed consent should not be included or continue in the study.

8.6 Confidentiality of records

The investigator must assure that the patients' anonymity will be maintained. Patients should not be identified by name on any documents submitted to the sponsor or during verbal communications. Patients will be identified with their initials and a protocol-assigned patient number.

The investigator will maintain all signed informed consent forms in strict confidence, and will maintain a separate log of patients' initials and hospital/clinic accession number.

All laboratory specimens and evaluation forms will be identified using only a coded number, patient number, patient initials and/or date of birth in order to maintain confidentiality. All records will be kept in a secured area in the clinical research unit. Computer entry and networking programs will be performed using coded numbers.

The patient will be informed that all clinical information is confidential and must consent to direct access to his/her original medical records and study data for study-related sponsor monitoring, audit, IRB/IEC review and regulatory inspection.

8.7 Discontinuation of study

The Sponsor reserves the right to discontinue the study at any time for clinical or administrative reasons. Such a termination must be implemented by the investigator, if instructed to do so by the Sponsor, in a time frame that is compatible with the wellbeing of study patients.

8.8 Compliance statement

The study will be conducted in accordance with standards that meet regulations relating to current Good Clinical Practice. These standards respect the following guidelines: current Good Clinical Practice; Consolidated Guideline (International Conference on Harmonization of Technical Requirements for the Registration of Pharmaceuticals for Human Use, May 1996); United States (US) Code of Federal Regulations (CFR) dealing with clinical studies (21 CFR parts 50, 54, 56, 312, and 314), and the Declaration of Helsinki.

8.9 Quality control

The sponsor, or its representative, will be responsible for implementing and maintaining quality assurance and quality control systems with written SOPs to ensure that the study is conducted and data are generated, documented (recorded), and reported in compliance with the protocol, cGCP and the applicable regulatory requirements.

9 Statistical Considerations

The clinical outcomes, laboratory, PK, and other safety data from all segments of the study will be analyzed descriptively. In addition to determining DLT and RP2D, results will be analyzed to

determine if a sufficient response signal and safety profile justifies further study. Descriptive statistical summaries for demographic and patient baseline characteristics will be produced, as well as statistical summaries of safety, efficacy and pharmacokinetic/pharmacodynamic results, where categories for statistical summaries will consist of the dose level and duration initially assigned for Parts 1 and 2 dose and schedule escalation, and the initial dose and duration in the Expansion Cohort (RP2D). In addition, exploratory analyses of both toxicity, response (ORR), Stable Disease (SD) and pharmacodynamic data will be performed for both the assigned and actual daily dose and duration of infusions, the actual number of days of treatment, and for cumulative exposure to study drug as expressed by the product sum of dose over time (area under the dose-time curve).

Disease Control Rate (DCR) defined as the proportion of patients with a confirmed Complete Response (CR), Partial Response (PR) or Stable Disease (SD) per RECIST v1.1 Duration of Response (DOR) defined from the first date a response is identified (either CR or PR) until the date of objective tumor progression per RECIST v1.1 Progression-Free Survival (PFS) defined as time from first dose of TK216 to objective tumor progression per RECIST v1.1 or death due to any cause, whichever occurs first.

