It is anticipated that 6 to 8 cohorts will be completed during the dose escalation segment of this trial. With the concurrence of the investigators and the study sponsor, further testing may be performed in up to 12 additional patients per dose level to refine the estimation of the MTD and RP2D at intermediate dose levels or to define a higher MTD and RP2D while using Cycle 1 primary supportive care prophylaxis (e.g., with growth factors, antidiarrheals, antiemetics) for bone marrow and/or gastrointestinal toxicities.

Additional cycles of therapy may be administered provided that the patient meets the following criteria on Day 1 of each cycle:

- ANC \geq 1,000/mm³
- Hemoglobin \geq 8.0 gm/dL (Blood transfusions are permitted.)
- Platelets \geq 50,000/mm³
- Non-hematologic toxicity recovered to \leq Grade 1 (or tolerable Grade 2)

Intra-patient dose escalation will be permitted during the dose escalation segment of this trial. Patients may have their dose of TK216 increased after they have completed 2 cycles of treatment at their assigned dose, assuming their initial dose was well tolerated and the subsequent cohort (at the next higher dose level) has been well tolerated through Cycle 1. At the investigator's discretion, the dose escalation can either take the form of an increase in daily dose with 7 days of dosing and 14 days of rest, or an increase of duration, with 14 days of dosing and 7 days of rest, but not both.

Other schedules of administration may be investigated after tolerability and PK data are acquired with this schedule.

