- initiation of continuous infusion via a central venous catheter.

4.2.2.12 Day 2 of Cycle 2 and 3, Continuation of Hospitalization (Cohorts 1, 2, 3)

On Day 2 of Cycle 2 and 3 of dose escalation Cohorts 1, 2 and 3, the procedures listed below will be performed:

- continuous infusion via a central venous catheter of study drug;
- vital signs
- clinical laboratory tests (hematology, clinical chemistries, coagulation, urinalysis);
- symptom-driven physical examination;
- 12-lead ECG done between 20 and 24 hours after starting the infusion on Day 1 of cycles 2 and 3 (to coincide with the PK sample);
- plasma PK sample taken between 20 and 24 hours after starting the infusion on Day 1 of cycles 2 and 3;
- concomitant medication check;
- adverse event assessment.

4.2.2.13 Day 3 of Cycle 2 and 3, Discharge from Hospital (Cohorts 1, 2, 3)

On Day 3 of Cycle 2 and 3 of dose escalation Cohorts 1, 2 and 3, prior to discharge from the hospital, the procedures listed below will be performed:

- continuous infusion via a central venous catheter of study drug;

- vital signs
- symptom-driven physical examination;
- clinical laboratory tests (hematology, clinical chemistries, coagulation, urinalysis);
- concomitant medication check;
- adverse event assessment.

4.2.2.14 **Days 4 through 7 of Cycle 2 and 3 (Cohorts 1, 2, 3)**

On Days 4 through 7 of Cycle 2 and 3 of dose escalation Cohorts 1, 2 and 3, the continuous infusion via a central venous catheter will continue as an outpatient. If the patient experiences any problems with the infusion, the site should be contacted.

4.2.2.15 **Day 8 of Cycle 2 and 3, Outpatient Visit (Cohorts 1, 2, 3)**

On Day 8 (+/- 2 days) of Cycle 2 and 3 of dose escalation Cohorts 1, 2 and 3, the patient will return for an outpatient visit, at which time the infusion will be discontinued and the following procedures will be performed:

- vital signs;
- weight;
- symptom-driven physical examination;
- 12-lead ECG prior to discontinuing the infusion;
- clinical laboratory tests (hematology, clinical chemistries, coagulation, urinalysis);
- concomitant medication check;
- adverse event assessment.

4.2.2.16 **Day 15 of Cycle 2 and 3, Outpatient Visit (Cohorts 1, 2, 3)**

On Day 15 (+/- 2 days) of Cycle 2 and 3 of dose escalation Cohorts 1, 2 and 3, the procedures listed below will be performed during an outpatient visit:

- clinical laboratory tests (hematology, clinical chemistries, coagulation);
- concomitant medication check;

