6.3.5.9 Pharmacokinetic Assessments, Schedule Escalation Cohorts, Cycle 1 (Cohorts 7, 8, 9)

During Cycle 1 only of the schedule escalation cohorts, PK assessments will be collected at the end of the cycle infusion, +/- 10 minutes, at the following time points:

- 1 hour prior to stopping the infusion;
- immediately prior to stopping the infusion;
- .5 hours (30 minutes) after stopping the infusion;
- 1 hour after stopping the infusion;
- 2 hours after stopping the infusion;
- 4 hours after stopping the infusion;

- and 8 hours after stopping the infusion.

For all cycles during the schedule escalation and expansion cohorts, a single PK assessment will be done at each of the following days, if the scheduled infusion is continuing: Days (+/- 1) 4, 8, 11, 15, 18, and 22.

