10.4 Pharmacokinetics

Pharmacokinetic variables will be summarized by dose group and time point.

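### Part 2 PK concentrations drawn after a dose change would be summarised under the patient's starting dose, and PK is left out of the planned analyses by actual dose

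*Combined protocol and SAP*

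**What the plan says.** Section 9 (Statistical Considerations) sets one grouping rule for "statistical summaries of safety, efficacy and pharmacokinetic/pharmacodynamic results". For the escalation parts, the "categories for statistical summaries will consist of the dose level and duration initially assigned for Parts 1 and 2 dose and schedule escalation". The next sentence adds a second look: "exploratory analyses of both toxicity, response (ORR), Stable Disease (SD) and pharmacodynamic data will be performed for both the assigned and actual daily dose". PK is not on that list.

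The sections devoted to PK do not settle the matter. Section 9.5 speaks of dose levels, and section 10.4 says "Pharmacokinetic variables will be summarized by dose group and time point". Neither says whether the dose meant is the one assigned at entry or the one being infused.

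Doses can change within a patient while sampling goes on:

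- **Part 2 increases (section 2.3).** After any well-tolerated cycle the daily dose may move up one level at the next cycle.
- **Reductions (section 2.6.1.1, Parts 1-3).** The dose may be lowered after Cycle 1 for drug-related toxicity.
- **Part 2 sampling (section 6.3.5.9).** "For all cycles during the schedule escalation and expansion cohorts, a single PK assessment will be done at each of the following days": Days 4, 8, 11, 15, 18 and 22, provided the infusion is still running.
- **Part 1 (section 2.2).** "Patients may have their dose of TK216 increased after they have completed 2 cycles of treatment at their assigned dose", on condition that "the subsequent cohort (at the next higher dose level) has been well tolerated through Cycle 1".

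**The concern.** A concentration during a continuous infusion depends directly on the rate being infused when the sample is drawn. Section 9 recognises that assigned and actual dose can part company, and provides for it with four kinds of data, but not with PK.

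Under the stated rule, a later-cycle mean for a dose group can mix patients still at the starting dose with patients above or below it. A rise between cycles could then be read as accumulation when it is only a dose increase.

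The vincristine question is the more exposed one. Section 1.2 makes PK of TK216 alone and with vincristine a secondary objective of Part 2. Section 2.3 allows vincristine only once Cycle 2 is complete, so all Part 2 combination samples come from Cycle 3 or later. Those are the cycles in which dose changes will have built up.

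**Working it through.** The plan states no figure on this point, so there is none to reproduce. The check sets the rules side by side and then illustrates the size.

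**1. Does the grouping rule reach PK?** Yes. Section 9 names PK/PD results in the sentence that defines the categories. Sections 9.5 and 10.4 are silent on assigned versus actual dose, so they do not override it.

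**2. Where do dose changes and PK sampling overlap?**

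| Part | Earliest within-patient increase | PK sampling after Cycle 1 | Overlap |
|---|---|---|---|
| 1 | Cycle 3, if the next cohort has cleared Cycle 1 (2.2) | One 20-24 h sample in each of Cycles 2 and 3 (4.2.2.12, 6.3.4.10) | At most the Cycle 3 sample |
| 2 | Cycle 2 (2.3) | Single samples in all cycles while infusing (6.3.5.9) | Direct, from Cycle 2 on |

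Reductions after Cycle 1 (2.6.1.1) add mislabelling in the other direction.

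**3. How narrow is the Part 1 overlap?** For Cohorts 1-3 the sample is the "plasma PK sample taken between 20 and 24 hours after starting the infusion on Day 1 of cycles 2 and 3"; Cohorts 4-6 have an equivalent one. Cohorts are sequential and cycles last 21 days. Counting from the start of the current cohort's last patient, and assuming no delays:

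- That patient's Cycle 3 begins at 2 × 3 = 6 weeks.
- The next cohort completes Cycle 1 no earlier than 3 + 3 = 6 weeks.

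The two only just meet for that last patient. Patients enrolled earlier would normally have started Cycle 3 already. The investigator may also lengthen the infusion instead of raising the dose, which leaves the rate at 20-24 h unchanged.

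**4. What is not touched?** Serial sampling belongs to Cycle 1: sections 4.2.2.1, 4.2.2.2 and 4.2.2.8 for Cohorts 1-3, sections 6.3.4.1, 6.3.4.2 and 6.3.4.6 for Cohorts 4-6, and section 6.3.5.9 for Part 2. Cycle 1 precedes any within-patient increase. Cmax, AUC, half-life and the dose-normalised ANOVA of section 9.5 therefore rest essentially on data at the assigned dose.

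**5. Illustrative size.** Assume concentrations proportional to dose. If k of n sampled patients have had their dose multiplied by f, the group mean at that time point changes by k(f − 1)/n. The plan gives no step size for Part 2. The 50% step of Part 1 (f = 1.5) is borrowed as an assumption.

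| Raised patients, k | n = 3 | n = 6 |
|---|---|---|
| 1 | 1 × 0.5/3 = 16.7% | 1 × 0.5/6 = 8.3% |
| 2 | 2 × 0.5/3 = 33.3% | 2 × 0.5/6 = 16.7% |
| 3 | 3 × 0.5/3 = 50.0% | 3 × 0.5/6 = 25.0% |

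One patient stepping down by the same ratio (f = 1/1.5 = 0.667) gives −0.333/3 = −11.1% for n = 3 and −0.333/6 = −5.6% for n = 6.

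**6. What this does to the vincristine comparison.** Take a group of 3 in which one patient moves up a 50% step at Cycle 2, and all three start vincristine at Cycle 3. With no interaction at all, the Cycle 3 mean exceeds the Cycle 1 mean by the same 16.7%, which would appear as higher exposure with vincristine.

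**The case against.** The strongest reply is that little of importance depends on these samples. The main PK parameters come from Cycle 1. Section 9.5 already plans dose-normalised Cmax and AUC. Section 2.3 has later Part 2 cohorts chosen on first-cycle results. PK is a secondary and mostly descriptive objective, section 7.4 has the administered dose in the eCRF, and section 10 promises listings of all data, so nothing is lost. This stands, and it limits the point to later-cycle concentrations.

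Two further replies stand only in part:

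- **Splitting by time point.** If the time points of section 10.4 are cycle-specific, Cycle 1 rows stay clean. Patients with and without a dose change still share the later-cycle cells.
- **The bar on simultaneous changes.** Section 2.3 forbids starting vincristine and raising the dose in the same cycle. It does not prevent an increase in Cycle 2 followed by vincristine in Cycle 3, or an increase after vincristine has begun.

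A reader might infer more than the documents support:

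- **That the choice of RP2D is distorted.** Section 2.3 ties it to the MTD or to target inhibition with acceptable safety. No stated rule uses later-cycle mean concentrations.
- **That the error could reach 33% to 100%, as after a doubling.** Doubling belongs to the accelerated phase of Part 1, where at most one sample per patient is exposed and the timing makes even that unlikely.
- **That escalated patients make up a large share of Cycle 3 samples.** The documents give no such count, and the Part 1 timing points the other way.

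**Conclusion.** The point holds for post-Cycle 1 concentrations, chiefly in Part 2. As written, section 9 files them under the starting dose whatever was being infused, and no section provides a PK summary by actual dose. The interpretations at risk are accumulation over cycles and the Part 2 comparison of PK alone and with vincristine. Part 1 is affected marginally, and the Cycle 1 parameters essentially not at all.

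The 17% (group of 3) and 8% (group of 6) for one raised patient are illustrations. They rest on dose-proportional PK, a borrowed 50% step, and every member of the group being sampled. The documents give no linearity data and no number of patients expected to change dose. Fewer patients at a later cycle would make one dose change weigh more; the extra patients that section 2.3 allows at a dose level would make it weigh less.

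**What to change.** - In sections 9, 9.5 and 10.4, state that PK concentrations after Cycle 1 are summarised by the TK216 daily dose being infused when the sample was taken, with cycle and vincristine use (yes/no) as further classifiers.
- Show dose-normalised concentrations alongside.
- Add PK to the analyses by actual dose in section 9.
- Keep the initially assigned grouping for safety and response.

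The cost is plan wording and table programming. The administered dose and any interruptions are already recorded in the eCRF (section 7.4). Dosing, sampling and patient management are unchanged.
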